7.1. Inclusion Criteria

Patients are eligible to be included in the study only if they meet **all** of the following criteria:

- [1] The patient signed an ICF and authorization for release of health information for research prior to any study-specific procedures being performed.
- [2] The patient is aged ≥ 18 years at study entry.
- [3] The patient has histologically confirmed diagnosis of locally advanced unresectable or metastatic STS not amenable to curative treatment with surgery or radiotherapy. Patients with a diagnosis of Grade 1 liposarcoma are eligible if there is histological or radiographic evidence of evolution to more aggressive disease. Patients with Kaposi's sarcoma and gastrointestinal stromal tumors (GIST) will be excluded.

Note: Evidence of disease progression is required for patients that are not newly diagnosed.

- [4] The patient has measurable or nonmeasurable but evaluable disease as defined by the Response Evaluation Criteria in Solid Tumors (RECIST 1.1, Eisenhauer et al. 2009; refer to [Attachment 6](#)). Tumors within a previously irradiated field will be designated as "nontarget" lesions unless progression is documented or a biopsy is obtained to confirm persistence at least 90 days following completion of radiotherapy.

- [5] The patient has a performance status 0-1 on the Eastern Cooperative Oncology Group (ECOG) scale (refer to [Attachment 4](#)).
- [6] The patient has not received any previous treatment with anthracyclines.
- [7] The patient may have had any number of prior systemic cytotoxic therapies for advanced/metastatic disease and are considered appropriate candidates for anthracycline therapy. All previous anticancer treatments must be completed ≥ 3 weeks (21 days) prior to first dose of study drug.
- [8] The patient has resolution of adverse events and of all clinically significant toxic effects of prior locoregional therapy, surgery, radiotherapy, or systemic anticancer therapy to \leq Grade 1, by National Cancer Institute - Common Terminology Criteria for Adverse Events (NCI-CTCAE) Version 4.0.

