Lesions with Prior Local Treatment:

- Tumor lesions situated at a previously irradiated area, or in an area subjected to other loco-regional therapy, are non-measurable unless there has been demonstrated progression in the lesion.

Baseline Documentation of Target and Non-Target Lesion***Target Lesions***

When more than 1 measurable lesion is present at baseline, all lesions up to a maximum of 5 lesions total (and a maximum of 2 lesions per organ) representative of all involved organs should be identified as target lesions and will be recorded and measured at baseline. Non-nodal Target lesions should be selected on the basis of their size (lesions with the longest diameter), be representative of all involved organs, and can be reproduced in repeated measurements. Measurable lymph nodes are target lesions if they meet the criteria of a short axis of ≥ 15 mm by CT scan. All measurements are to be recorded in the case record form (CRF) in millimeters (or decimal fractions of centimeters [cm]).

Nontarget Lesions

All other lesions (or sites of disease) are identified as nontarget lesions (chosen based on their representativeness of involved organs and the ability to be reproduced in repeated measurements) and should be recorded at baseline. Measurement of these lesions are not required but should be followed as ‘present,’ ‘absent,’ or in rare cases ‘unequivocal progression.’ In addition, it is possible to record multiple nontarget lesions involving the same organ as a single item on the CRF (for example, multiple liver metastases recorded as 1 liver lesion).

Lymph nodes with short axis ≥ 10 mm but < 15 mm should be considered nontarget lesions. Nodes that have a short axis < 10 mm are considered nonpathological and are not recorded or followed.

Specifications by Methods of Measurement

All measurements should be recorded in metric notation, using a ruler or calipers if clinically assessed. All baseline evaluations should be performed as closely as possible to the beginning of treatment and never more than 4 weeks before the beginning of the treatment.

The same method of assessment and the same technique should be used to characterize each identified and reported lesion at baseline and during follow-up. Imaging-based evaluation is

should always be done rather than clinical examination unless the lesion(s) being followed cannot be imaged but are assessed by clinical exam.

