It is assumed that at each protocol-specified time point, a response assessment occurs. (When no imaging/measurement is done at all at a particular time point, the patient is not evaluable (NE) at that time point.) Table 1 provides a summary of the overall response status calculation at each time point for patients who have *measurable disease* at baseline.

Table 1. Time Point Response: Patients with Target (\pm Nontarget) Disease

Target Lesions	Non-Target Lesions	New Lesions	Overall Response
CR	CR	No	CR
CR	Non-CR/non-PD	No	PR
CR	Not evaluated	No	PR
PR	Non-PD or not all evaluated	No	PR
SD	Non-PD or not all evaluated	No	SD
Not all evaluated	Non-PD	No	NE
PD	Any	Yes or No	PD
Any	PD	Yes or No	PD
Any	Any	Yes	PD

Abbreviations: CR = complete response; PR = partial response; SD = stable disease.; PD = progressive disease; NE = inevaluable.

Table 2 is to be used when patients have *nonmeasurable* disease only.

Table 2. Time Point Response: Patients with Nontarget Disease Only

Nontarget Lesions	New Lesions	Overall Response
CR	No	CR
Non-CR/non-PD	No	Non-CR/non-PD ^a
Not all evaluated	No	NE
Unequivocal PD	Yes or No	PD
Any	Yes	PD

Abbreviations: CR = complete response; PD = progressive disease ; NE = inevaluable.

^a non-CR/non-PD is preferred over SD for nontarget disease.

Frequency of Tumor Re-Evaluation

A baseline tumor evaluation must be performed within 4 weeks before patient begins study treatment. Frequency of tumor re-evaluation while on and adapted to treatment should be protocol-specific and adapted to the type and schedule of treatment. In the context of Phase 2 studies where the beneficial effect therapy is not known, follow-up every 6-8 weeks is reasonable. Normally, all target and non-target sites are evaluated at each assessment using the same method. However, bone scans may need to be repeated only when CR is identified in target disease or when progression in bone is suspected.

Confirmatory Measurement/Duration of Response

Confirmation:

The main goal of confirmation of objective response in clinical trials is to avoid overestimating the response rate observed.

In *randomized trial* (Phase 2 or 3) or studies where SD or progression is the primary endpoints, confirmation of response is not required.

In the case of SD, follow-up measurements must have met the SD criteria at least once after start of treatment at a minimum interval not less than 5 weeks measured from randomization..

Duration of Overall Response

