5.2.1. Definitions of Analysis Variables

Definitions of efficacy, safety, and PRO analysis variables are listed in Section 5.2.1.1, Section 5.2.1.2, and Section 5.2.1.3, respectively. Other variables are listed below alphabetically.

- **Age (years):** $(\text{Informed Consent Date} - \text{Date of Birth} + 1)/365.25$.
Note. Average days in a year = 365.25, reflecting the Julian Year of 3 years with 365 days each and 1 leap year of 366 days. Birth month and day are imputed to be 01 July because only birth year is collected through eCRF.
- **Baseline measurement** is the last non-missing measurement prior to first dose for safety analyses, and the last non-missing measurement prior to randomization for demographic and efficacy analyses.
- **Duration** is calculated as:
 - Duration (days): $(\text{End Date} - \text{Start Date} + 1)$
 - Duration (weeks): $(\text{End Date} - \text{Start Date} + 1)/7$
 - Duration (months): $(\text{End Date} - \text{Start Date} + 1)/30.4375$
Note. Days in months = $(1/12) \times \text{average number of days in a year}$
 - Duration (years): $(\text{End Date} - \text{Start Date} + 1)/365.25$
- **Duration of disease** is defined as months from first diagnosis of cancer to randomization.

- **Measurable disease (Yes/No)** is defined as yes for patients with at least 1 target lesion based on radiographic assessment data collected at baseline. If no target lesions are present, then patients would be categorized as a No.
- **Study Day:** Study day indicates the number of days the patient has been receiving study treatment. It is calculated as assessment date – first dose date + 1 day if the assessment is done on or after the first dose day. If the assessment is done prior to the first dose day, study day will be calculated as assessment date – first dose date. Date of first dose is defined as Study Day 1.

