5.2.1.1. Efficacy Analysis Variables

Definition of efficacy analysis variables are listed.

Overall survival (OS) is defined for each patient as the time from the date of randomization to the date of death from any cause. If the patient is alive at the cutoff date for the analysis (or was lost to follow-up without a confirmed date of death), OS will be censored for analysis on the last date the patient was known to be alive.

Progression-free survival (PFS) is defined for each patient as the time from the date of randomization to the first date of radiologic disease progression (as defined by Response Evaluation Criteria In Solid Tumors, Version 1.1 [RECIST v.1.1]) based on investigator assessments or death due to any cause. [Table JGDJ.5.1](#) defines the rules of censoring to be applied to PFS. In addition, sensitivity analyses of PFS will be performed using different rules for censoring (as defined by [Table JGDJ.5.2](#)).

Table JGDJ.5.1. Censoring Rule of PFS Primary Analysis

Situation	Event / Censor	Date of Event or Censor
Tumor progression or death	Event	Earliest date of PD or death
No tumor progression and no death	Censored	Date of last adequate radiological assessment or date of randomization (whichever is later)
unless		
No baseline radiological tumor assessment available	Censored	Date of randomization
No adequate postbaseline radiological tumor assessment available and death reported after 2 scan intervals following randomization	Censored	Date of randomization
New anticancer treatment started and no tumor progression or death within 14 days	Censored	Date of adequate radiological assessment prior to (start of new therapy +14 days) or date of randomization (whichever is later)
Tumor progression or death documented immediately after 2 or more consecutive missing scan intervals following last adequate radiological tumor assessment or randomization (whichever is later)	Censored	Date of last adequate radiological assessment prior to the missing assessment or date of randomization (whichever is later)

Abbreviations: CR = complete response; PD = progressive disease; PR = partial response; SD = stable disease.

- a Symptomatic deteriorations (that is, symptomatic progressions, which are not radiologically confirmed) will not be considered as disease progressions.
- b Adequate radiological tumor assessment refers to an assessment with one of the following responses: CR, PR, SD, or PD.

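### Two SAP response lists omit Non-CR/non-PD, so read as written they mis-censor PFS and miscount DCR and DDC for stable patients with nontarget disease only

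*SAP*

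**What the plan says.** **Eligibility.** Protocol 7.1, criterion [4]: "The patient has measurable or nonmeasurable but evaluable disease". SAP 5.2.1 recognises the same patients in its measurable-disease variable: "If no target lesions are present, then patients would be categorized as a No".

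**Response label.** Protocol Attachment 6 has a separate time-point table (Table 2) for patients with nontarget disease only. Its possible outcomes are CR, Non-CR/non-PD, NE and PD. There is no SD row, and the table's footnote reads "non-CR/non-PD is preferred over SD for nontarget disease".

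**Adequate scan.** SAP 5.2.1.1, Table JGDJ.5.1, footnote b: "Adequate radiological tumor assessment refers to an assessment with one of the following responses: CR, PR, SD, or PD". Three rows of that table depend on this definition:
- a patient with neither PD nor death is censored at the last adequate assessment, or at randomization if there is none;
- a patient with "No adequate postbaseline radiological tumor assessment available" who dies beyond two scan intervals is censored at randomization;
- a patient who starts new anticancer treatment, with no PD or death within 14 days, is censored at the preceding adequate assessment or at randomization.

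**DCR and DDC.** SAP 5.2.1.1 defines both by a best overall response of CR, PR or SD. SAP 5.11.3.3 repeats this for DCR.

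**The concern.** The protocol gives one group of eligible patients a response that neither SAP list contains. The lists are separate and have separate effects: footnote b governs censoring, and the DCR and DDC definitions govern who counts as controlled. A patient scanned on schedule for months with stable nontarget disease could be treated for PFS as never assessed after baseline, and for DCR as not controlled.

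PFS in the ITT population is H2 in the alpha-controlled family (SAP 5.11.1), so its censoring should not rest on a coding choice that the plan leaves open. DCR and DDC are secondary objectives. DCR is compared between arms with the Cochran-Mantel-Haenszel test and also summarized at the interim (SAP 5.17.1), but it lies outside the family (SAP 5.6).

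**Working it through.** **1. Following the rules for one patient.** The two-scan window is 2 × 6 weeks + 14 days = 98 days (Protocol 8.1.1; Table JGDJ.5.1, footnote c). Take a nontarget-only patient with Non-CR/non-PD at every scan from day 42 to day 252.

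| Course | Footnote b as written | Non-CR/non-PD counted as adequate |
|---|---|---|
| Alive without PD | censored day 0 | censored day 252 |
| Death on day 280, no PD | censored day 0 | event day 280 |
| New therapy on day 260, no PD or death within 14 days | censored day 0 | censored day 252 |

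A patient with a single Non-CR/non-PD scan on day 42 who then dies on day 80, or has PD on day 84, is an event under both readings.

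**2. Sensitivity analyses (Table JGDJ.5.2).** None generally restores the event-free patient, and SA 2 part B again uses the last adequate assessment. SA 2 part A recovers patients on new therapy who later have an event. SA 3 recovers late deaths only if the performed scans are treated as missed visits. None concerns DCR or DDC.

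**3. DCR.** The plan gives no figure to reproduce and no nontarget-only share, so shares of 2, 5 and 10% of 460 (about 9, 23 and 46 patients) are assumed. Assume also exponential PFS with the SAP design medians of 4.5 and 7.15 months (footnote to Table JGDJ.5.5) and disease control when PFS exceeds 6 weeks, i.e. 42/30.4375 = 1.38 months:
- control: 0.5^(1.38/4.5) = 0.809
- experimental: 0.5^(1.38/7.15) = 0.875

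The understatement of DCR is the share times this probability. The change in the between-arm difference is the share times (0.875 − 0.809) = 0.066. DDC exclusions are 230 × share × probability, summed over arms.

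| Share | DCR understated, control / experimental (points) | Change in difference (points) | Patients lost from DDC |
|---|---|---|---|
| 2% | 1.6 / 1.7 | 0.13 | 3.7 + 4.0 ≈ 8 |
| 5% | 4.0 / 4.4 | 0.33 | 9.3 + 10.1 ≈ 19 |
| 10% | 8.1 / 8.7 | 0.66 | 18.6 + 20.1 ≈ 39 |

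With the first scan at week 5 or week 7, the probabilities are 0.838/0.895 or 0.780/0.856. At a 10% share this moves either arm's figure by about 0.3 points at most.

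**4. PFS.** This was simulated with 400,000 patients per arm, the same medians, scans every 6 weeks with a 1-week window either side, and administrative censoring uniform over 12 to 36 months (assumed). A performed scan was not treated as missing. Counting only patients event-free at cutoff, 4.7% (control) and 13.0% (experimental) of the subgroup are censored at day 0: about 1, 2 or 4 patients in total at 2, 5 or 10%. If 20% of PFS events are deaths without PD and 10% of patients start new therapy (both assumed), the proportions are 20% and 30%, or about 2, 6 or 11 patients.

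The ITT PFS hazard ratio moves from 0.6303 to 0.6317, 0.6338 or 0.6373 (event-free group only), so by about 0.001, 0.003 to 0.004, or 0.007. The other scenarios give equal or smaller shifts. In these scenarios the shift is toward 1, because more event-free follow-up is removed from the experimental arm. In 3,000 simulated trials at the one-sided 0.025 node, power is 0.996 with correct censoring against 0.995 at every share. With 20% deaths and 20% new therapy it falls from 0.994 to 0.989 at the 10% share.

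**5. OS and ORR.** OS uses no scan data, and Non-CR/non-PD is not a response, so neither changes.

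**The case against.** The strongest reply is that the literal reading is not the intended one. The imaging row of the treatment-period schedule (Protocol Attachment 1) uses the same CR/PR/SD shorthand when it says who is scanned until progression, while Protocol 8.1.1 and 8.1.2 require scans for everyone until PD. There the shorthand plainly covers all progression-free patients. The evident purpose of footnote b is to exclude unevaluable or unperformed scans. A preference over SD is a labelling preference, and best overall response comes from an algorithm whose specification is not in these documents. This stands as evidence of probable intent. It does not supply the missing mapping.

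Four stronger readings might be inferred, and the documents do not support them:
- **That footnote b causes the DCR and DDC loss.** It does not; that loss comes from the separate response lists in the DCR and DDC definitions.
- **That every stable nontarget-only patient lacks an adequate scan.** A later PD scan is on the list. If a performed scan is not a missing interval, as the wording of the last row of Table JGDJ.5.1 suggests, PD found at that scan remains an event.
- **That all lesions in treated fields swell this group.** Attachment 6 says such lesions "are non-measurable unless there has been demonstrated progression in the lesion", but criterion [4] gives irradiated lesions a second route to target status, through biopsy-confirmed persistence.
- **That the late-death problem carries over to every endpoint borrowing Table JGDJ.5.1.** Time to any progression and time to new metastasis censor at death by their own rule.

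The Appendix 1 flow chart, which governs patients meeting several censoring criteria, is not visible. Combined cases, such as new therapy followed by late death, are therefore left open and not held against the plan.

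**Conclusion.** The point holds and is minor. Two SAP lists, followed as written, give a wrong result for an eligible group that the protocol labels differently. The textual gap is certain; how the records will actually be coded is not known.

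The size rests on an assumed nontarget-only share with no anchor in the documents. Over 2 to 10%, and with a first scan at six weeks, absolute DCR is understated by at most about 1.6 to 8.7 points per arm. These are upper bounds for each share, because patients with no evaluable scan miss DCR under either reading. The upper end belongs to the 10% assumption alone. The between-arm DCR difference moves by under 1 point and the ITT PFS hazard ratio by at most about 0.007, with power still about 99%.

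A reader might infer a risk of a false-positive PFS result. The figures do not support that: the modelled shift is toward 1. That direction assumes equal proportions of deaths without PD and of new therapy in the two arms.

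**What to change.** Before unblinding of the aggregate data, make two separate changes to the SAP:

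1. In footnote b of Table JGDJ.5.1, add Non-CR/non-PD for nontarget-only disease, or state that it maps to SD, for every endpoint that uses the table.
2. In the DCR and DDC definitions, count Non-CR/non-PD as disease control when it meets the minimum that Attachment 6 already sets for SD: "at least once after start of treatment at a minimum interval not less than 5 weeks measured from randomization".

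The cost is one or two lines of text and a small programming change. No new data are needed.

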8.1.2. Postdiscontinuation Follow-Up Period Assessments

Postdiscontinuation short-term and long-term follow-up assessments will be conducted as described in the Study Schedule ([Attachment 1](#)). Adverse event (AE) information will be collected until at least 30 days after the last dose of study treatment. After the 30-day short-term follow-up visit, only new and ongoing SAEs deemed related to study treatment will be collected.

Long-term follow-up will continue as long as the patient is alive and has not withdrawn consent to follow-up or the study has completed (as defined in [Section 8.1.3](#)).

For patients who discontinue study treatment for any reason without objectively measured PD, imaging studies and tumor assessments are obtained every 6 weeks (± 7 days), irrespective of treatment cycles as calculated from randomization, until documented progression.

For patients that discontinue study treatment after objectively measured PD, the following information will be collected every 2 months (± 7 days) for the first 2 years, then every 6 months (± 14 days) until the patient's death, or overall study completion:

- details on all subsequent anticancer treatment (start/stop dates and treatments administered)
- first post-study treatment disease progression date
- survival status

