- c The 2-scan interval is counted from the date of last adequate tumor assessment to the date of next 2 scheduled tumor assessments plus 14 days (adjusted by tumor assessment window).
- d Refer to flow chart in [Appendix 1](#) if a patient meets multiple censoring criteria.
- e If there are multiple dates associated with 1 assessment, the assessment date will be set to the first date when the overall response is PD and the last date otherwise.

Table JGDJ.5.2. Censoring Rules for PFS Sensitivity Analysis Definitions

Sensitivity Analysis Definition #	Situation	Date of Progression or Censor	Censored / Progressed
SA 1: Count symptomatic deterioration as progression	Radiographic documented progression or symptomatic deterioration	Date of documented progression or date of symptomatic deterioration, whichever occurred first	Progressed
SA 2: Ignore new anticancer treatment	New anticancer treatment (systemic therapy) started before radiographic documented progression or death	A) Date of radiographic documentation of progression or death, whichever is earlier B) Last adequate radiological assessment if no radiographic documented progress or death occurred	A) Progressed B) Censored
SA 3: Ignore missing tumor assessment	Death or radiographic documented progression after ≥ 2 consecutively missed tumor assessment visits	Date of radiographic documentation of progression or death, whichever is earlier	Progressed
SA 4: Treat lost to follow up as progression	Patient is lost to follow-up without radiographic documented progression or death	Date of next scheduled postbaseline radiological assessment at or after becoming lost to follow-up	Progressed

Abbreviations: PFS = progression-free survival; SA = Sensitivity Analysis.

Progression-free survival 2 (PFS2) is defined as the time from the randomization date to the date of disease progression on next-line treatment, or death due to any cause, whichever occurs first. [Table JGDJ.5.3](#) defines the rules of censoring to be applied to PFS2. Note that disease progression on next-line treatment in this study will be recorded by investigators without details of corresponding radiologic assessment results. In the event that the date of disease progression on next-line treatment is reported only to the nearest month, the date will be imputed for analysis (assumed to have occurred on the 15th day of the reported month).

Table JGDJ.5.3. Censoring Rules of PFS2 Analysis

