PD on study therapy	Situation			Event / Censor	Date of Event or Censor
	PD after end of study therapy but prior to next line of treatment	PD on next line of treatment	Death		
Yes	No	Yes	Yes / No	Event	Event at PD date on next line of treatment
Yes	No	No	No	Censored	Censoring at the date PD-free on next line of treatment
Yes	No	No	Yes	1) Event 2) Censored	Event at death date if no further treatment, otherwise censoring at the date PD-free on next line of treatment
No	Yes	Yes	Yes / No	Event	Event at PD date on next line of treatment
No	No	Yes	Yes / No	Censored	Censoring at start of next line of treatment
No	Yes / No	No	No	Censored	Censoring at the date PD-free on next line of treatment
No	Yes	No	Yes	1) Event 2) Censored	Event at death date if no further treatment, otherwise censoring at the date PD-free on next line of treatment
No	No	No	Yes	Censored	Censoring at start of next line of treatment

Time to any progression (censoring for death without progression) is defined identically to PFS, except that the time to any progression will be censored at the date of death if there is no prior or concurrent radiologic disease progression. Otherwise, censoring follows the rules described in [Table JGDJ.5.1](#).

Time to any new metastasis (censoring for death and/or for progressive disease (PD) due to increased sum of target lesions) is defined for each patient as the time from the date of randomization to the first date of radiographic documentation of 1 or more new lesions. Time to any new metastases will be censored at the first date of radiologic disease progression if that progression was based solely on an increased sum of target lesions (without new lesions). If there is no radiologic disease progression, time to any new metastases will be censored following the rules of [Table JGDJ.5.1](#), with the exception that censoring will be applied at the date of death (if no previous event or censoring).

New-metastases-free survival (nMFS) is defined for each patient as the time from the date of randomization to the first date of radiographic documentation of 1 or more new lesions, or to the date of death from any cause (whichever occurs first). nMFS will be censored at the first date of radiologic disease progression if that progression was based solely on an increased sum of target lesions (without new lesions). Otherwise, nMFS will be censored for analysis in a manner analogous to PFS (following the rules of [Table JGDJ.5.1](#)).

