5.6. Multiple Comparisons/Multiplicity

The independent data monitoring committee (IDMC) will perform unblinded interim safety and efficacy analyses. Family-wise type I error is controlled for this study's key efficacy outcomes (OS, PFS, and ORR) as described in Section 12.1 of the study protocol and Section 5.11 of this SAP. Regarding all other study analyses, multiplicity of statistical error is not controlled or adjusted for in any way.

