5.11.3.2. Key Secondary Efficacy Analyses

For PFS, the same analyses used for the analyses of the primary endpoint OS will be performed. In addition, as sensitivity analyses, the primary PFS analysis will be repeated using different PFS censoring rule as defined in [Table JGDJ.5.2](#), to evaluate whether and to what extent the conclusion of the PFS analysis under the primary definition would be affected under the different censoring rules.

This comparison of PFS using the same method as that for the primary analysis of PFS will be considered inferential only in case of significant results for OS analysis (that is, as a gatekept analysis so as not to inflate the overall type I error rate).

The main PFS analysis will also be repeated for a subset of patients started monotherapy.

If PFS analysis is significant, then testing on ORR will be conducted. Objective tumor response (CR+PR) rate (ORR) will be reported along with exact confidence bounds (CI: 95%) and compared using the Cochran-Mantel-Haenszel test adjusting for the stratification variables. A sensitivity sensitivity analysis on ORR will be performed to consider only confirmed response (using 4-week interval for confirmation).

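### The PFS2 censoring table discards deaths that the PFS2 definition counts, and gives some patients a censoring date that cannot exist

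*SAP*

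**What the plan says.** SAP 5.2.1.1 defines PFS2 as "the time from the randomization date to the date of disease progression on next-line treatment, or death due to any cause, whichever occurs first", with no exception for any kind of death. It then refers to Table JGDJ.5.3 for censoring. The table's eight rows are not numbered in the SAP; they are counted here from the top.

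- **Rows 3 and 7** (progression on study therapy, or after it but before the next line; no progression on the next line; died): "Event at death date if no further treatment, otherwise censoring at the date PD-free on next line of treatment".
- **Row 8** (no progression at any stage; died): always censored, with the single date rule "Censoring at start of next line of treatment".
- **Rows 2 and 6** (alive, no progression on the next line): censored at the date the patient was free of progression on the next line, with no provision for patients who never started one.

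For PFS, the first row of Table JGDJ.5.1 counts progression or death as an event at the "Earliest date of PD or death", subject to listed exceptions. Protocol 10.1.4 lists PFS2 among the additional efficacy measures and leaves event and censoring definitions to the SAP.

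**The concern.** The definition and the table give different answers for the same patient. In rows 3 and 7 an observed death is turned into a censored time because the patient had begun further treatment. In row 8, a patient who dies without progression and without a next line is censored at a date that never occurred. Yet rows 3 and 7 count a death without further treatment as an event, and Table JGDJ.5.1 would normally count the row 8 death as a PFS event. One death can therefore be a PFS event but not a PFS2 event.

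Censoring because a patient died breaks the assumption that censored patients resemble those still at risk. It lengthens the Kaplan-Meier medians, and it biases the hazard ratio if such deaths are more frequent in one arm. In rows 2, 6 and 8 the programmer must also choose dates that the SAP does not give. SAP 5.11.3.2 plans alternative censoring for PFS ("the primary PFS analysis will be repeated using different PFS censoring rule"); none is listed for PFS2.

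**Working it through.** The documents give no PFS2 event count or power to reproduce, so the first check is logical.

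**1. Definition against table, path by path**

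| Row | Patient path | Definition | Table |
|---|---|---|---|
| 1, 4 | Earlier PD, then PD on next line | Event at that PD | Same |
| 3, 7 | Earlier PD, no next line, died | Event at death | Same |
| 3, 7 | Earlier PD, next line started, no PD recorded on it, died | Event at death | **Censored** |
| 8 | No PD, no next line, died | Event at death | **Censored, no such date** |
| 2, 6 | Alive, no next line | Censored | **Censored, no such date** |
| 8 | No PD, switched therapy, died | Event at death | Censored at switch |
| 5 | No PD, switched therapy, PD on next line | Event at that PD | Censored at switch |

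The last two paths also depart from the definition. They parallel the new-therapy rule in Table JGDJ.5.1, which applies to patients with "no tumor progression or death within 14 days" of starting new treatment, and may be intended. They are not counted as errors. That rule cannot explain rows 3 and 7, whose patients progressed before the next line.

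Nothing else repairs the bold rows. Table JGDJ.5.2 concerns PFS only. SAP 5.4 completes partial dates but does not supply dates for events that never happened.

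**2. Share of events affected**

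All rates here are assumptions:
- d = share of first events that are deaths without PD and with no next line: 5-15%
- u = share of progressors who start a next line: 60-70%
- q = share of next-line events that are deaths without recorded PD: 20-50%

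With complete follow-up and no switching before PD, rows 3 and 7 censor (1 − d) × u × q of the defined events:
- minimum: 0.85 × 0.60 × 0.20 = 10.2%
- maximum: 0.95 × 0.70 × 0.50 = 33.3%
- if q were only 10%: 0.85 × 0.60 × 0.10 = 5.1% to 0.95 × 0.70 × 0.10 = 6.7%

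Row 8 leaves a further share d, 5-15%, without a usable date.

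**3. Effect on the estimates (rows 3 and 7 only)**

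The simulation used 100,000 patients per arm. First events were exponential with the design PFS medians of 4.5 and 7.15 months (SAP Table JGDJ.5.5, footnote). The remaining inputs are assumed: next line starts 1 month after PD; median 3.5 months to the next-line event; median 6 months to death after PD with no next line; administrative censoring at 18-36 months; censoring 0-2 months before death in rows 3 and 7; row 8 deaths kept as events.

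| Equal rates in both arms | By definition | By table |
|---|---|---|
| Events lost | – | 10.3-33.7% |
| Control median (months) | 10.2-11.0 | 11.0-14.1 |
| Olaratumab median (months) | 13.1-14.1 | 14.3-18.2 |
| HR | 0.692-0.705 | 0.686-0.704 |

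Varying the censoring lag, the two post-progression medians and the follow-up gave a loss of 10-35% and an HR shift of at most 0.01.

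**4. Unequal q between arms**

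With q of 20/30, 30/40 or 40/50% in the two arms, the HR of 0.69-0.70 becomes 0.63-0.66 when the higher share is on olaratumab and 0.73-0.75 when it is on control. Each 10-point difference moves the HR by 0.04-0.07. No HR is given for row 8, because the table supplies no date to analyse.

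**The case against.** **Another reading of rows 3 and 7.** Further treatment could mean therapy beyond the next line. A death on next-line therapy would then be an event, and only patients who moved to a later line without recorded progression would be censored. The wording does not exclude this, and the loss figures above depend on the other reading. It is a strained reading, because the branch most naturally separates patients with and without a next line. It would also still censor deaths that the definition counts.

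**Censoring deaths can be a design choice.** Table JGDJ.5.1 censors deaths after two or more missed scan intervals. Next-line progression is recorded without radiologic detail (SAP 5.2.1.1), and scans are not required after progression (Protocol 10.1.2). A death may therefore follow unrecorded progression, and an event placed at death would come late. That limitation is real. But the SAP does not give this reason, rows 3 and 7 apply however recently the patient was assessed, and the argument does not reach row 8.

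**Rows 2, 6 and 8 may only be drafting gaps.** For row 8 the definition itself supplies an event date. Even so, the table says censored and has no branch for patients without a next line.

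**The size is assumed, and the endpoint is low in the hierarchy.** Both are true. A lower q roughly halves the minimum loss, equal rates leave the HR almost unchanged, and nothing in the documents suggests that q differs by arm.

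**Conclusion.** The concern holds. Followed literally, Table JGDJ.5.3 gives a PFS2 analysis that contradicts its own definition in rows 3 and 7, and cannot be programmed for patients with no next line in rows 2, 6 and 8. The contradiction is certain from the text. Its numerical effect is not: apart from the two design PFS medians, every rate above is an assumption, and neither size nor direction is fixed by the documents. The likeliest harm is overstated medians in both arms; a distorted HR needs an imbalance between arms.

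The reach is limited. PFS2 is one of 13 additional measures in Protocol 10.1.4, and SAP 5.6 places it outside error control: "Regarding all other study analyses, multiplicity of statistical error is not controlled or adjusted for in any way". Every affected death still counts in OS, and OS, PFS, ORR and the type I error are untouched. The importance is minor to moderate, but it should be corrected because PFS2 will be reported with a stratified log-rank test, Cox model and Kaplan-Meier estimates (SAP 5.11.3.3).

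**What to change.** Amend Table JGDJ.5.3 before the sponsor is unblinded:

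1. In rows 3 and 7, and in row 8 for patients with no next line, count death without earlier next-line progression as an event at the death date.
2. In rows 2 and 6, censor living patients who never started a next line at the last date known alive and free of next-line progression.
3. For patients who switched without progression (row 5 and the matching part of row 8), either follow the definition or write the exception into it, and report the other option as a labelled PFS2 sensitivity analysis.

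The cost is one SAP table and its derivation program. Item 1 needs death dates and item 2 last-known-status dates, both already collected for OS. Item 3 has a data limit. Protocol 8.1.2 schedules next-line treatment and progression dates only after objective progression: "For patients that discontinue study treatment after objectively measured PD, the following information will be collected". Next-line progression dates may therefore be incomplete for patients who switched earlier, and the SAP should say so when it makes that choice.
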